### **9.7.1.2.5 Sensitivity Analysis**

A sensitivity analysis using multiple imputations or tipping point analysis was to be conducted on the ITT population to assess the likelihood that missing data could bias the conclusion of the primary endpoint (i.e., proportion of subjects achieved a GCS score  $\geq$  13 at or prior to 90 minutes post-randomization) of the study.

#### **9.7.1.2.6 Multicenter Clinical Trials**

This study was a multicenter clinical trial. All the data collected from the different study centers was to be presented as a by-subject listing.

#### **9.7.1.2.7 Multiple Comparisons and Type I Error Rate Multiplicity Adjustments**

For the primary endpoint only one (1) hypothesis was to be tested, hence there was to be no adjustment for Type I error rate.

For the secondary endpoints, the closed test procedure was to be used to protect the trial-wise error rate. [REDACTED].

#### **9.7.1.2.8 Covariates and Prognostic Factors**

For efficacy analyses, baseline values were to be used as covariates in the analysis models.

#### **9.7.1.2.9 Stratification Factors**

The randomization for the study was stratified by study center. This stratification was used to ensure a balanced distribution of subjects among the two treatment groups.

#### **9.7.1.2.10 Subgroup Analysis**

Subgroup analyses were to be conducted for the predefined stratification factors presented in [Section 9.7.1.2.9](#) above. Additional subgroup analysis for all the efficacy endpoints was to be conducted using the subgroup of subjects that did not require endotracheal intubation at post-randomization.

#### **9.7.1.2.11 Standard Calculations**

##### Age

Age was to be calculated as the number of completed years between the date of randomization and the subject's birth date as per the formula listed below:

$$\text{Age (years)} = \text{integer of } [(date \text{ of randomization} - date \text{ of birth}) / 365.25 + 0.5]$$

##### Change from Baseline

Change from baseline for a given measurement was to be calculated using below formula.

Change From Baseline = Post baseline result at time t – Baseline result

Percent Change from Baseline

Percent change from baseline for a given measurement was to be calculated using below formula.

Percent Change =  $[(\text{Post baseline result at time t})/\text{Baseline result} - 1] * 100$

Temperature

For summary purposes, temperature was expressed in Celsius. Entries made in Fahrenheit ( $^{\circ}\text{F}$ ) was to be converted to Celsius ( $^{\circ}\text{C}$ ) using below formula.

Temperature ( $^{\circ}\text{C}$ ) =  $(\text{Temperature} ({}^{\circ}\text{F}) - 32) * (5/9)$

Time to first rectal temperature  $\leq 37^{\circ}\text{C}$  and  $\leq 38^{\circ}\text{C}$

Time (minutes) to first rectal temperature  $\leq 37^{\circ}\text{C}$  was to be calculated using below formula.

Time to first rectal temperature  $\leq 37^{\circ}\text{C}$  =

Time of first rectal temperature  $\leq 37^{\circ}\text{C}$  – Time of baseline rectal temperature

Time (minutes) to first rectal temperature  $\leq 38^{\circ}\text{C}$  was to be calculated using below formula.

Time to first rectal temperature  $\leq 38^{\circ}\text{C}$  =

Time of first rectal temperature  $\leq 38^{\circ}\text{C}$  – Time of baseline rectal temperature

### 9.7.1.3 Analyses Populations

#### 9.7.1.3.1 Intent-to-Treat (ITT) Population

The Intent-to-Treat (ITT) population was defined as all randomized subjects who received any study treatment. Subjects who achieved a GCS total score of  $\geq 13$  prior to receiving any study treatment were to be excluded from the ITT population. The ITT population was to be the primary population for the analysis of the primary and secondary efficacy endpoints.

### **9.7.1.3.2 Per Protocol (PP) Population**

The Per Protocol (PP) population was defined as [REDACTED]

### **9.7.1.3.3 Safety Population**

The Safety population was defined as all randomized subjects who received any study treatment (SOC with Ryanodex or SOC only). This population was to be used for analysis of all safety endpoints using actual treatment received.

### **9.7.1.4 Analysis of Efficacy Data**

All inferential statistical analysis was to be based on a two-sided test with a Type I error rate of 0.05.

The primary analyses of the primary and secondary efficacy endpoints were to be conducted on the ITT population. [REDACTED]

#### **9.7.1.4.1 Primary Endpoint**

The primary efficacy endpoint for this study was cumulative incidence of subjects achieving a GCS score  $\geq 13$  at or prior to 90 minutes post-randomization.

The number and percentage of subjects who achieved a GCS score  $\geq 13$  at or prior to 90 minutes post-randomization was to be presented by treatment arm. The [REDACTED] adjusting for baseline GCS score was to be used to analyze the percentage of subjects achieving GCS score  $\geq 13$  at or prior to 90 minutes post-randomization and the 95% CI for the treatment difference and p-value for the treatment effect was to be reported.

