2. SYNOPSIS

Name of Sponsor/Company: Eagle Pharmaceuticals, Inc.	
Name of Finished Product: Ryanodex® (EGL-4104) (dantrolene sodium) for injectable suspension)	
Name of Active Ingredient: Dantrolene sodium	
Protocol: EGL-4104-C-1801	
Title of the Study: Phase 3, Multi-Center, Double-Blind, Randomized, 2-Arm, Parallel Study to Assess the Efficacy and Safety of Ryanodex® (EGL-4104) as Adjuvant Treatment in Subjects with Exertional Heat Stroke (EHS)	
Investigator: [name], MHPE	
Study Center: Four (4) Emergency Departments in the Makkah region of Kingdom of Saudi Arabia	
Publications (reference): None	
Studied Period: (first subject enrolled): 21 August 2018 (last subject completed): 13 August 2019	Phase of Development: Phase 3
Objectives: Primary Objective: To evaluate the efficacy of Ryanodex® for the treatment of exertional heat stroke (EHS), administered as adjunctive treatment to current standard of care (SOC), compared to administration of SOC only.	
Secondary Objective: To evaluate the safety and tolerability of Ryanodex for the treatment of EHS, administered as adjunctive treatment to current SOC.	
Methodology: Study EGL-4104-C-1801 was a Phase 3, multi-center, double-blind, randomized, 2-arm parallel study of Ryanodex for the adjuvant treatment of EHS administered intravenously (IV), to current	

SOC.

Standard of care (SOC) for the treatment of EHS is defined as effective body cooling and supportive measures, which is to be implemented as quickly as available after diagnosis of heat stroke.

Due to the life-threatening nature of EHS, rapid assessment for inclusion into the study and subsequent immediate treatment was to occur.

Number of Subjects (Planned and Analyzed):

Planned: 100 **Analyzed:** 17

Diagnosis and Main Criteria for Inclusion:

Male or non-pregnant female subjects were to be entered into this study if they were diagnosed with known or suspected EHS as evidenced by meeting all of the following criteria at Screening:

- Subjects had a core body temperature obtained rectally of $\geq 40.0^{\circ}\text{C}$ (104.0°F);
- In the judgment of the Investigator, the subject was likely to be at least 18 years of age
- Subject had recent history or suspected recent history (prior 24 hours) of performing intense physical activity (exertional activity)
- The subject had impaired consciousness level as evidenced by a GCS score < 13
- The subject had tachycardia (heart rate ≥ 100 bpm).

Diagnosis and Main Criteria for Exclusion:

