A Statistical Analysis Plan (SAP) was finalized prior to database lock. Statistical methods in the SAP were to take precedence over those described in this protocol. All collected study data was to be presented in subject data listings. Statistical analyses was to be performed using SAS® for Windows, version 9.4 or later.

Sample Size:

A total of 100 (50 per treatment group) eligible subjects were planned to be randomized in this study. The nQuery Advisor 6.01 software was to be used for this sample size calculation. The sample size calculation was based on the assumption that 50% of subjects who receive SOC therapy and Ryanodex was to achieve a GCS score ≥ 13 at or prior to 90 minutes post-randomization, compared with only 14.3% of subjects who receive SOC therapy alone. Under the above

assumptions, 50 subjects per treatment group were to be required to meet the Type I error rate of 0.05, 2-sided and over 95% statistical power to detect the difference between treatments; for a total of 100 subjects for the study.

Baseline:

Baseline body temperature was to be the first rectal temperature $\geq 40.0^{\circ}\text{C}$ taken during the Screening Phase. Baseline results for other study assessments were to be the value closest in time to the baseline rectal temperature and prior to randomization. The SAP may specify additional data handling rules.

Analysis Populations:

The safety population was to include all randomized subjects who received any study treatment (SOC only or SOC plus Ryanodex). The safety population was to be used to analyze all safety endpoints using actual treatment received.

The Intent-to-Treat (ITT) population was to include all randomized subjects who received any study treatment and was to be used as the primary efficacy population. Subjects who achieved a GCS total score of ≥ 13 prior to receiving any study treatment were to be excluded from the ITT population.

The Per Protocol population (PP) was to include all ITT subjects who met all inclusion/exclusion criteria, had a baseline and at least 1 post-baseline GCS total score, and had no major protocol deviations that could affect the efficacy assessments.

The ITT and Per Protocol populations were to be analyzed using planned treatment assignments. Classification of subjects with respect to the ITT, PP, and Safety populations was to be conducted prior to the database lock.

Efficacy Analysis:

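### Randomisation is stratified by study center, but no readable text puts center in the primary model; if it is left out, the test is somewhat conservative when centers differ materially, with no added false positives (minor)

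*SAP*

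**What the plan says.** - **Design.** SAP 9.7.1.2.9: "The randomization for the study was stratified by study center". The Protocol synopsis lists "Four (4) Emergency Departments in the Makkah region of Kingdom of Saudi Arabia".
- **Primary analysis.** SAP 9.7.1.4.1 has a redacted method name followed by "adjusting for baseline GCS score was to be used to analyze the percentage of subjects achieving GCS score". It then says that the "95% CI for the treatment difference and p-value for the treatment effect was to be reported".
- **Covariates.** SAP 9.7.1.2.8, with no redaction mark: "baseline values were to be used as covariates in the analysis models". Center is not named.
- **Other uses of center.** SAP 9.7.1.2.6: "All the data collected from the different study centers was to be presented as a by-subject listing". SAP 9.7.1.2.10: "Subgroup analyses were to be conducted for the predefined stratification factors".
- **Protocol.** The synopsis names a logit model for the primary endpoint and no covariate. It also says "Statistical methods in the SAP were to take precedence over those described in this protocol", so its silence on center is weak evidence.

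The readable plan therefore uses center for randomisation, listings and subgroups, but not for the primary inference.

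**The concern.** Stratifying by center forces the arms to be nearly balanced within each center. If response rates differ between centers, the two arm estimates then move together, and their difference varies less than a model without center assumes. The model overstates the standard error, so the test rejects less than 5% of the time under the null and the CI is too wide. The trial has paid for a precision gain in its design and does not collect it in its analysis. What is at stake is some power and interval width for the primary endpoint.

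**Working it through.** **1. The plan's own figure.** Inputs (SAP 9.7.2): 50 per arm, 50% versus 14.3%, two-sided 0.05.
- Pooled rate (0.5 + 0.143)/2 = 0.3215; null SE = sqrt(2 × 0.3215 × 0.6785/50) = 0.0934.
- Alternative SE = sqrt((0.25 + 0.143 × 0.857)/50) = 0.0863.
- z = (0.357 − 1.96 × 0.0934)/0.0863 = 2.01, so power is 97.8%. Fisher's exact test gives 96.6%.

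The stated power of over 95% reproduces.

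**2. Direction and mechanism.** With equal centers, exact balance within center and no other covariate, under the null:

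true SE / naive SE = sqrt(1 − B/[p(1−p)]), where B is the between-center variance of the response rate and p its mean.

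| Assumed center rates (%) | p | B | p(1−p) | SE ratio | Implied size 2[1 − Φ(1.96/ratio)] |
|---|---|---|---|---|---|
| 5, 10, 15, 27 | 0.1425 | 0.0067 | 0.1222 | 0.97 | 4.4% |
| 5, 15, 40, 68 | 0.32 | 0.0595 | 0.2176 | 0.85 | 2.2% |
| 2, 2, 3, 50 | 0.1425 | 0.0426 | 0.1222 | 0.81 | 1.5% |

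A simulation with permuted blocks of 4 within center (block size assumed) agrees: unadjusted chi-square size was 4.7%, 2.3% and 1.7%. Without stratification (simple randomisation) the Wald test omitting center stayed at 3.9% to 4.5% in every set of rates, so the conservatism comes from balance within center.

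**3. Size of the effect at N = 100.** Assumed: GCS 3 to 12 with median 5, GCS effect 0.7 log-odds per SD, control rate 14.3%, four centers of 25, arms balanced within center, normal center effects. To read the SD scale, ignore GCS and solve for the intercept that gives a 14.3% mean (−1.88, −2.11, −2.44). Centers one SD either side of the middle then have rates of about 8% and 20% (SD 0.5), 4% and 25% (SD 1.0), and 2% and 28% (SD 1.5). There were 30,000 null and 8,000 alternative trials per setting, and both models were fitted to the same trials. P-values are from the score test; the CI is for a standardised risk difference.

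| Center log-odds SD | 0 | 0.5 | 1.0 | 1.5 |
|---|---|---|---|---|
| Size, GCS only (%) | 5.4 | 5.0 | 4.4 | 3.8 |
| Size, GCS + center (%) | 5.9 | 5.8 | 5.8 | 5.6 |
| Power at 50%, GCS only (%) | 98.7 | 98.6 | 98.7 | 97.6 |
| Power at 50%, GCS + center (%) | 98.8 | 98.9 | 99.1 | 98.9 |
| Median CI width at 50%, GCS only (points) | 32.8 | 32.8 | 32.7 | 32.5 |
| Median CI width at 50%, GCS + center (points) | 32.8 | 32.1 | 30.5 | 28.5 |
| CI coverage at 50%, GCS only (%) | 94.6 | 95.0 | 96.2 | 96.6 |
| CI coverage at 50%, GCS + center (%) | 94.6 | 94.5 | 94.7 | 94.5 |

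- With centers of 50/24/16/10 the power gains at 50% are 0.2, 0.1, 0.6 and 1.2 points.
- Part of each gain is only the higher size. At matched size the gain at 50% is at most about 0.8 point.
- If the treated rate were 35% (assumed), raw power goes from 72.6% to 80.6% at SD 1.5, but the matched-size gain is +3.1 points. At SD 0, 0.5 and 1.0 it is −0.5, −0.2 and +1.0, within a simulation error of roughly 1 point.

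**4. The achieved size.** With 9 versus 8 subjects and assumed centers of 5/4/4/4, center dummies push size to 10.6–12.0% (score) or 18.1–21.2% (likelihood ratio). The GCS-only score test stays at 3.8–5.7%.

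**The case against.** **The gap sits on a redaction.** The blacked-out method name in SAP 9.7.1.4.1 is where a center-stratified method would appear, text in 9.7.1.4 is also hidden, and 9.7.1 describes itself as highlights. This stands. A reader might infer that the plan certainly omits center; the documents do not prove that. Omission remains the natural reading, because the unredacted covariate and multicenter sections do not name center as a model term and the legible adjustment is GCS alone.

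**The consequence is small.** This also stands. The only clear matched-size gain needs a true effect below the planned one and a center SD of 1.5. Nothing in the documents suggests that spread among four emergency departments in one region.

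**The remedy pushes size the other way.** Partly right. The adjusted score test has size of about 5.5–6.2%. At 14.3% of 100 there are about 14 events under the null for five non-intercept terms. With centers of 40/30/20/10 and rates of 2, 2, 3 and 50%, the adjusted likelihood-ratio test reached 9.0%, against 3.8% without center. Omitting center at this event count is therefore defensible, and adding it needs care over the test and over small centers.

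**Exact balance is assumed.** No block size is given in the readable text. Large or incomplete blocks would weaken the conservatism.

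**Conclusion.** The point holds as a minor one, on condition that the redacted words do not already include center. Randomisation uses a factor that the readable primary model leaves out. The result is a test that falls below nominal size (about 4.4% at SD 1.0, 3.8% at SD 1.5) and a CI about 2 to 4 points wider than needed (32.7 − 30.5 = 2.2; 32.5 − 28.5 = 4.0). At SD 0.5 or less nothing measurable is lost. At the planned effect, score-test power differs by 0.1 to 0.6 point at SD 0 to 1.0 and about 1.3 points at SD 1.5, and exceeds 95% with or without center. The center spread, center sizes, GCS effect and within-center balance are all assumptions.

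Three stronger readings are tempting and not supported:
- *That ignoring the stratification inflates false positives.* In every setting above, size without center was below size with center. The 5.4% at SD 0 is a small-sample effect, also present with center (5.9%).
- *That the trial was underpowered because of this.* The score-test figures at the planned effect do not show it.
- *That the 17-subject analysis should be redone with center.* Center terms would badly inflate its size.

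**What to change.** **For the planned 100 subjects**, unless the redacted text already does so, specify in SAP 9.7.1.4.1 and 9.7.1.2.8:
- a logit model with treatment, baseline GCS and study center;
- the p-value from the score test;
- a 95% CI for the standardised risk difference from the same model, with the delta-method SE multiplied by sqrt(n/(n − p)) and a t quantile;
- pooling of very small centers (for example, fewer than 10 subjects) by a rule set before unblinding.

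**For the achieved 9 versus 8**, add no center terms and keep the prespecified analysis. Any within-center exact or re-randomisation test is an optional sensitivity analysis, labelled post hoc.

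**Cost.** SAP wording and one variable that is already recorded. The downsides to accept are:
- score-test size of about 5.5–6.2%, slightly above nominal;
- no gain if centers do not differ;
- dependence on the choice of test. At SD 1.5 and the planned effect, Wald power falls from 94.5% to 94.0% with centers of 50/24/16/10 and from 91.6% to 90.5% with 70/20/6/4 (92.0% if the two smallest are pooled). The score test rises from 97.4% to 98.6% and from 96.0% to 97.8%;
- dependence of the CI on its correction: coverage with center is 93.0–93.9% without the small-sample factor and 94.1–95.1% with it;
- disagreement between this CI and the score test on significance in at most 1.6% of trials.

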#### **9.7.1.4.2 Secondary Endpoints**

As discussed in [Section 9.7.1.2.7](#), to protect the type I error rate for the secondary endpoints, the closed test procedure was to be used. Discussed below are the approaches that were to be taken for each of the secondary endpoints. These endpoints are presented in the order that were to be tested.

**9.7.1.4.2.1 Cumulative incidence of subjects who achieve a GCS score  $\geq 13$  at planned time points**

The number and percentage of subjects who achieved a GCS score  $\geq 13$  at each planned time point was to be presented by treatment arm.

[figure not shown]

.

**9.7.1.4.2.2 Actual values, changes from baseline, and percent changes from baseline in GCS scores over time**

Actual values, changes from baseline and percent changes from baseline in GCS scores were to be calculated (see [Section 9.7.1.2.11](#) for calculation). Descriptive summary of number of observations, mean, standard deviation, median, and minimum and maximum values was to be presented.

### **9.7.1.5 Planned Analysis for Safety Data**

All safety analyses were to be conducted using the Safety population. All data collected was to be summarized according to the variable type.

For continuous variables, data was to be summarized by treatment using n, mean, standard deviation, minimum, and maximum values. For categorical variables, data was to be summarized by treatment using frequency and percentage. No inferential statistics were planned.

### 9.7.1.5.1 Adverse Events

Adverse events were to be coded using the most recent version of Medical Dictionary for Regulatory Activities (MedDRA). Treatment Emergent AE's (TEAE) were defined as events which started on or after the start date and time of randomization, or which worsened after the start date and time of randomization. TEAEs were to be summarized by treatment group, System Organ Class, and preferred term. The following TEAE summaries were to be provided:

- Overall (i.e., regardless of severity or relationship to treatment)
- By severity grade (mild, moderate, or severe)
- By investigators causality assessment (related, possibly related, probably related or unrelated)

In addition, separate summaries of serious adverse events, and adverse events resulting in study discontinuation will be presented.

clinically significant) and Abnormal (clinically significant)) with counts and percentages

A large rectangular area of the page is completely blacked out, indicating the redaction of sensitive data. The redaction is approximately 750 pixels wide and 440 pixels high, starting below the text 'clinically significant) and Abnormal (clinically significant)) with counts and percentages'.

### 9.7.2 Determination of Sample Size

A total of 100 (50 per treatment group) eligible subjects were planned to be randomized in this study. The nQuery Advisor 6.01 software is used for this sample size calculation. The sample size calculation is based on the assumption that 50% of subjects who receive SOC therapy and Ryanodex will achieve a GCS score  $\geq 13$  at or prior to 90 minutes post-randomization, compared with only 14.3% of subjects who receive SOC therapy alone.

Under the above assumption, 50 subjects per treatment group were required to meet the Type I error rate of 0.05, 2-sided and over 95% statistical power; for a total of 100 subjects for the study.

[Figure 9-3](#) depicts the statistical power and sample size based on the above specified assumptions with a Type I error rate of 0.05 and 2-sided test.

**Figure 9-3: Study Sample Size Estimation**
